6.1.7.1.2 Dates and times

Partially or completely missing dates may be imputed for the following reasons:

- Classification of AEs as TEAEs;
- Classification of medications as past, prior, or concomitant medications;
- Durations of AEs.
- Imputed dates will not be shown in listings. All dates will be displayed as reported in the database.

The following rules will be applied for partially or completely missing start dates:

- If year, month and day are all missing then assign the date of first dose of IMP. If an imputed start date is after the specified end date, then assign January 01 of the year of the end date, or the date of screening if this is later (if the latter imputation results in an end date that is earlier than the start date, then use January 01).
- If month and day are missing, and year is:

- the same as the year of the first dose of IMP then assign the month-day of first dose of IMP. If the imputed start date is after the specified end date, then assign January 01, or the month-day of screening date if this is later (if the latter imputation results in an end date that is earlier than the start date, then assign January 01);
- not the same as the year of the first dose of IMP then assign January 01.

- If only day is missing, and month-year is:
 - the same as the month-year of the first dose of IMP then assign the day of first dose of IMP. If the imputed start date is after the specified end date, then assign first day of the month, or the day of screening date if this is later (if the latter imputation results in an end date that is earlier than the start date, then assign first day of the month);
 - not the same as the month-year of the first dose of IMP then assign the first day of the month.

The following rules will be applied for partially or completely missing stop dates:

- If only the month and year are specified, then use the last day of the month. If an imputed stop date is after last contact date, then assign last contact date as the stop date;
- If only the year is specified, then use December 31 of the known year. If an imputed stop date is after last contact date, then assign last contact date as the stop date;
- If the stop date is completely unknown, then use discharge date or data cut-off date. Discharge date refers to the date of the end of study visit for completed participants or the date of discontinuation for participants that were withdrawn. For any AEs with known start date after the date of discontinuation, the date of last contact will be used as the discharge date. For participants still ongoing in the study at the time of the data cut-off, and for whom no discharge date is available, the date of the data cut-off will be used instead of the discharge date.

Any medication with a start date on the first dosing date and time unknown, will be assumed to be concomitant.

Imputed AE dates will be used for the calculation of duration of AEs as described in [Table 6–2](#).

Table 6–2: Calculation Rules for Duration of AEs

Data availability	Onset date	Outcome date	Calculation rules
Complete data	D1	D2	$\text{Duration} = D2 - D1 + 1 \text{ d}$
Start date partially or completely missing	--	D2	$\text{Duration} \leq D2 - D0 + 1 \text{ d}$ Notes: D0 is imputed start date per above rules.

Data availability	Onset date	Outcome date	Calculation rules
End date partially or completely missing	D1	--	For ongoing AE: Duration \geq D3 – D1 d For resolved AE: Duration \leq D3 – D1 d Notes: D3 is imputed end date per above rules.
Start and end date partially or completely missing	--	--	For ongoing AE: Duration \geq D3 – D0 d For resolved AE: Duration \leq D3 – D0 d Notes: D0 is imputed start date and D3 is imputed end date per above rules.

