5.6.2 Adverse Events

5.6.2.1 Data considerations

Adverse events will be recorded from the time of informed consent until study completion. All AEs will be coded (see [Section 5.1.1.5](#)).

In addition, AEs will be classified according to the Common Terminology Criteria for Adverse Events (CTCAE) Version 5 or later for severity. For any AEs where it is not possible to provide a CTCAE grading, the events will be assessed using a standard intensity classification (mild, moderate and severe). For the purpose of the tabulations all CTCAE severity classifications will be mapped to a mild/moderate/severe grade as described below:

Grade: Intensity

- Grade 1 - Mild
- Grade 2 - Moderate
- Grade 3, 4, 5- Severe

These will be tabulated together with the AEs that were not classified according to CTCAE criteria i.e., all Grade 1 AEs as per CTCAE criteria will be included in the ‘mild’ category together with those AEs classified as mild as per the ‘standard’ intensity classification. In the case a mapped standard intensity classification per above rule is different from the standard intensity classification on CRF, the worst case will be used as the standard intensity classification (i.e., an AE with Grade 1 and moderate as intensity classification will be classified into moderate).

Any AE that occurred during the study will be defined as “**any AE**”.

A TEAE is defined as an AE starting on or after the time of first administration of IMP or any unresolved event already present before the first administration of IMP that worsens in intensity following exposure to treatment up to the end of the Treatment Period and including the 8-week (56 days) SFU. Adverse events starting before the date of the first administration of IMP or after SFU will not be considered TEAEs. Such events will be listed only.

Where dates are missing or partially missing, AEs will be assumed to be treatment-emergent unless evidence exists that does not allow the AE to be treatment-emergent. Handling of missing dates for classification of AEs as TEAEs is described in [Section 6.1.7.1.2](#).

The following rules will be used to assign a TEAE to a study period:

- **Treatment Period:** a TEAE will be assigned to the Treatment Period for the tabulations if the start date of the event is on or after the date of the first administration of IMP on Day 1, up to 7 days following the final dose of IMP;

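### SAP Table 6-2 gives an ongoing adverse event with a missing start date a minimum duration that the imputed start cannot guarantee

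*SAP*

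**What the plan says.** SAP 6.1.7.1.2 (Dates and times) sets the imputation rules for partial dates and then applies them to durations: "Imputed AE dates will be used for the calculation of duration of AEs as described in" Table 6-2.

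**Start date, D0**
- Wholly missing: "If year, month and day are all missing then assign the date of first dose of IMP".
- Only the day missing, in the month of first dose: "the same as the month-year of the first dose of IMP then assign the day of first dose of IMP".
- Only the day missing, in any other month: "not the same as the month-year of the first dose of IMP then assign the first day of the month".
- Only the year known: the month and day of first dose if the year matches, otherwise 1 January.
- If the imputed start falls after a stated end date, an earlier date is substituted.

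**End date, D3:** "If the stop date is completely unknown, then use discharge date or data cut-off date". For a completer, the discharge date is the End of Study visit.

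**Table 6-2**
- Row labelled "Start date partially or completely missing", end known (D2): duration ≤ D2 − D0 + 1.
- Start known (D1), end missing: ≥ D3 − D1 if ongoing, ≤ D3 − D1 if resolved.
- Both missing: ≥ D3 − D0 if ongoing, ≤ D3 − D0 if resolved. The note to this row is "D0 is imputed start date and D3 is imputed end date per above rules".

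SAP 5.6.2.1 adds two relevant conventions. The first is "Adverse events will be recorded from the time of informed consent until study completion". The second is that AEs with missing or partial dates are presumed treatment-emergent unless there is evidence to the contrary.

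**The concern.** A valid lower bound on duration needs the latest date on which the event could have started; a valid upper bound needs the earliest. The start-date rules produce one date, chosen so that an undated AE is classified as treatment-emergent. Table 6-2 then uses that date in both directions. In the last row the same quantity, D3 − D0, is a maximum if the AE resolved and a minimum if it is ongoing.

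The ≥ is sound in the row above, where the start is known and only the end is open. It does not carry over once the start is also unknown. A late true start shortens the duration and continuation past D3 lengthens it, so D3 − D0 bounds it in neither direction.

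At stake is a statement about individual events: that an ongoing AE with no recorded onset has lasted at least since first dose, or since the first of a month or year. Imputed dates are not displayed, so wherever such a duration is shown, the date behind the inequality would not be visible.

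**Working it through.** **Inputs**
- Doses are 7 days apart (nominal; Protocol Table 1-1, footnote on dosing interval), over 24 weeks. With 24 doses the last falls on Day 1 + 23 × 7 = 162.
- The End of Study visit is 8 weeks after the final dose (SAP 1.2): Day 162 + 56 = 218.
- Screening lasts up to 42 days (SAP, Study periods).
- Elapsed duration is counted as in Table 6-2's own complete-data row: end − start + 1.

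The SAP gives no worked duration to reproduce, so its rules are applied as written.

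**Lower bound, ongoing AE, start wholly missing**
- D0 = Day 1 and D3 = Day 218, so the table states duration ≥ 218 − 1 = 217 days.
- Onset on Day 218 gives 218 − 218 + 1 = 1 day elapsed. Onset on Day 1 gives 218 days.
- Elapsed time reaches 217 days only for onset on Day 1 or Day 2. It falls short for 216 of the 218 possible onset days on or after first dose.
- This count already assumes onset on or after first dose, so the presumption of treatment emergence does not rescue the bound. If onset back to consent is allowed, the elapsed range is 1 to 218 + 42 = 260 days.

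**Lower bound, ongoing AE, month known** (illustrative dates: first dose 10 March 2022, End of Study 13 October 2022, AE start given as June)
- D0 = 1 June. From 1 June to 13 October is 30 + 31 + 31 + 30 + 12 = 134 days, so the table states ≥ 134.
- Elapsed time runs from 106 days (onset 30 June: 105 + 1) to 135 days (onset 1 June). It is short of 134 for 28 of the 30 possible onset days.
- A valid lower bound from the latest possible start is ≥ 106 days.

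**Upper bound, start wholly missing, resolved on Day 30**
- D0 = Day 1, so the table states ≤ 30 − 1 + 1 = 30 days.
- With onset at consent, 42 days before first dose, the duration is 30 + 42 = 72 days. The excess is 42 days.
- With onset on or after first dose, 30 days is a correct maximum.

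**Upper bound, month known and equal to the month of first dose**
- First dose 20 March, start given as March, end 25 March: the table states ≤ 25 − 20 + 1 = 6 days. Onset on 3 March gives 25 − 3 + 1 = 23 days.
- The largest excess is the calendar day of first dose minus 1: here 20 − 1 = 19 days, and at most 31 − 1 = 30 days.

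The imputed-end rows also omit the + 1 used elsewhere in the table. That is a separate one-day matter and does not drive any conclusion here.

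**The case against.** **An ongoing AE continues past D3, so its total duration may well exceed D3 − D0.** This is right. A reader might infer that the ≥ statement is simply false, and the documents do not support that: it may turn out true. What stands is that the recorded data do not establish it, and a reported bound should follow from the data.

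**Undated AEs are presumed treatment-emergent.** This answers most of the upper-bound point. Under that presumption the first dose is the earliest start and the ≤ in the known-end row is coherent. The SAP also substitutes an earlier date when the stated end precedes the imputed start. A reader might infer that every ≤ bound is wrong. In fact, with the end known, the bound holds when D0 is the earliest possible date or when onset was truly on or after first dose. It fails only for a pre-dose onset, which is possible because AEs are collected from consent. The presumption does not help the ≥ bound.

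**D3 − D0 is at least the longest the event can have lasted so far.** It is not, once pre-dose onset is admitted: elapsed time can reach 260 days against the 217 stated.

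**The 217-versus-1 case is an extreme.** Agreed. It needs day, month and year of onset all to be missing for an event beginning at the final visit, although AEs are recorded throughout follow-up. The June example shows the same defect in a milder form.

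**Nothing important uses these durations.** Largely true. The outputs in SAP 5.6.2.2 include no summary of AE duration and specify no duration column. A reader might infer that the safety tables or the AE listings are wrong as planned; the documents do not show that. Reported dates are displayed as recorded, so the missing onset itself would be visible.

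**The rules match other studies in the programme.** The SAP amendment table gives this as the reason for the current duration rules. It is a reason to raise the point at programme level, but it does not make the bound valid.

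**Conclusion.** The point holds for the last row of Table 6-2: for an ongoing AE whose start is partially or completely missing, D3 − D0 is not a guaranteed minimum. For a nominal completer with wholly unknown onset, the table states at least 217 days where as little as 1 day may have elapsed. With a later month known, the June example states 134 days where 106 is supportable.

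The upper bounds that take the first dose as D0 are a secondary matter. They are conditional on treatment-emergent onset, and a pre-dose onset would exceed them by up to 30 days when the month is known. The figure is up to 42 days when the start is wholly missing or only the year is known.

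Day 218, the 42-day consent interval and the calendar examples are nominal or illustrative. The direction of the lower-bound problem does not depend on them.

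The consequence is small. It reaches only reported durations of AEs with missing start dates among 12 participants, and the number of such AEs is not given. Incidence tables, TEAE classification and efficacy results are unchanged. It is worth correcting because the rule, followed as written, yields an unsupported statement and the correction is cheap.

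**What to change.** 1. Keep the present imputed start dates for classifying TEAEs.
2. In the last row of Table 6-2, for ongoing AEs, compute the ≥ bound from the latest possible start: the last day of the reported month or year, but not after last contact. Leave duration blank when the start is wholly unknown.
3. For the ≤ bounds that now use the first dose as D0, either use the earliest possible start (first day of the reported month or year, not before consent; consent if wholly missing), or add a note that the bound assumes onset on or after first dose.

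The cost is a short edit to Table 6-2, with earliest- and latest-start definitions added to SAP 6.1.7.1.2 for durations only, and a minor programming change. No new data are needed. If the table is shared across the rozanolixizumab programme, the same edit should be considered there, since changing it here alone would depart from the common convention.

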6.1.7.2 Handling of repeated and unscheduled measurements

All repeated and unscheduled measurements will be presented in the listings, where applicable. The following general rules will apply to all repeated and unscheduled measurements:

- For repeated or unscheduled measurements obtained prior to the first dose of IMP the latest non-missing value (scheduled or unscheduled) will be used in the calculation of descriptive statistics (ie, Screening and/or Baseline);
- For repeated or unscheduled measurements obtained at the designated Baseline visit and prior to the first dose of IMP, the latest non-missing value (scheduled or unscheduled) will be defined as the Baseline;
- For repeated or unscheduled measurements obtained at any time point after the first dose of IMP, the scheduled values (if non-missing) will always be used in the calculation of changes from Baseline and for the descriptive statistics (ie, in summaries by time point). If repeated scheduled values are obtained at any time point, the latest non-missing will be used.

See [Section 5.6.3.1](#) for the rules applied to repeated lab results.

See [Section 5.6.3.4](#) for the rules applied to ECG triplicate measurements.

6.1.8 Treatment Compliance

Not applicable. The number of infusions will be recorded as detailed in [Section 5.6.1](#).

6.1.9 AEs of Special Interest

Potential Hy's Law, defined as $\geq 3 \times \text{ULN}$ ALT or AST with coexisting $\geq 2 \times \text{ULN}$ total bilirubin ($> 35\%$ direct bilirubin) in the absence of $\geq 2 \times \text{ULN}$ ALP, with no alternative explanation for the biochemical abnormality must always be reported to UCB as an AESI (ie, without waiting for any additional etiologic investigations to have been concluded).

6.2 Appendix 1: RBANS

To be added.

6.3 Appendix 2: mRS

The mRS is a commonly used scale for measuring the degree of disability or dependence in the daily activities of people who have suffered a stroke or other causes of neurological disability. The scale runs from 0 (perfect health) to 6 (death).

[figure not shown]
Modified Rankin Scale

MODIFIED RANKIN SCALE (MRS)

Patient Name: _____
Rater Name: _____
Date: _____

Score	Description
0	No symptoms at all
1	No significant disability despite symptoms; able to carry out all usual duties and activities
2	Slight disability; unable to carry out all previous activities, but able to look after own affairs without assistance
3	Moderate disability; requiring some help, but able to walk without assistance
4	Moderately severe disability; unable to walk without assistance and unable to attend to own bodily needs without assistance
5	Severe disability; bedridden, incontinent and requiring constant nursing care and attention
6	Dead
TOTAL (0-6): _____	

6.4 Appendix 3: Classification of the SF-36v2 questionnaire

This document contains confidential information
and is the property of UCB.

[figure not shown]
Table 6–3: SF-36v2® Health Survey Acute, United States

This

Confidential

[figure not shown]
Page 46 of 60

This document is a draft and is not intended for distribution outside the company.

[figure not shown]

This document applies to the EU only

This document is a draft and is not intended for distribution outside the company.

This document is for internal use only

6.5 Appendix 4: Markedly abnormal criteria for Rozanolixizumab program

The following criteria will be applied in the determination of marked abnormalities for laboratory assessment values. They are based on Version 5 of the Common Terminology Criteria for Adverse Events (CTCAE) grade 3 or higher criteria unless otherwise noted. If both high and low criteria are shown for a parameter, the criteria should be summarized separately in tabular or graphical data summaries.

Table 6-4: Hematology

Parameter	Unit (conventional)	Unit (standard)	Marked Abnormality Criteria
Hemoglobin	g/dL	g/L	<8.0 g/dL; <80 g/L
WBC (Leukocytes) ¹	$10^9/L$	$10^9/L$	Low: <2.0 $\times 10^9/L$
			High: >30 $\times 10^9/L$
Lymphocytes Absolute	$10^9/L$	$10^9/L$	Low: <0.5 $\times 10^9/L$
			High: >20 $\times 10^9/L$
Neutrophils Absolute	$10^9/L$	$10^9/L$	<1.0 $\times 10^9/L$
Platelets	$10^9/L$	$10^9/L$	<50.0 $\times 10^9/L$

¹WBC (Leukocytes) markedly abnormal high criterion is not based on Version 5 CTCAE Grade 3 or higher criteria. Due to the mechanism of action of RLZ, the safety alert is related to infection risk which would be identified by a lower cut-point than the standard which is related to acute leukemias. A markedly abnormal high cut-point >30 $\times 10^9/L$ is applied to flag leukocytosis (George 2012).

Table 6-5: Chemistry

Parameter	Unit (conventional)	Unit (standard)	Marked Abnormality Criteria
AST (SGOT)	U/L	U/L	>5.0 \times ULN
ALT (SGPT)	U/L	U/L	>5.0 \times ULN
ALP (Alkaline Phosphatase)	U/L	U/L	>5.0 \times ULN
GGT (Gamma Glutamyl Transferase)	U/L	U/L	>5.0 \times ULN
Bilirubin (Total)	mg/dL	umol/L	>3.0 \times ULN if Baseline value is normal; >3.0 \times Baseline value if Baseline is abnormal
Albumin	g/dL	g/L	<2 g/dL; <20 g/L
Creatinine	mg/dL	umol/L	>3.0 \times ULN
Estimate glomerular filtrate rate (eGFR) ¹	$mL/min/1.73\text{ m}^2$	$mL/min/1.73\text{ m}^2$	eGFR <29 $mL/min/1.73\text{ m}^2$
C reactive protein (CRP) ²	mg/L	mg/L	>10 mg/L
Calcium	mg/dL	mmol/L	Low: Corrected serum calcium ³ of <7.0 mg/dL; <1.75 mmol/L

			High: Corrected serum calcium ³ of >12.5 mg/dL; >3.1 mmol/L
Immunoglobulin G ⁴	(g/L)	(g/L)	≤1 g/L
Potassium	mmol/L	mmol/L	Low: <2.5 mmol/L
			High: >6.0 mmol/L
Sodium	mmol/L	mmol/L	Low: <125 mmol/L
			High: >155 mmol/L
Glucose ⁵	mg/dL	mmol/L	Low: <40 mg/dL; <2.2 mmol/L
			High: > 250 mg/dL; >13.9 mmol/L
Total Cholesterol	mg/dL	mmol/L	>400 mg/dL; >10.34 mmol/L
Triglycerides	mg/dL	mmol/L	>500 mg/dL; >5.7 mmol/L

Abbreviations: ALT = alanine aminotransferase; AST = aspartate aminotransferase; dL = deciliter; GGT: gamma-glutamyl transferase; L = liter; mg = milligram; mmol = millimoles; µg = microgram; U = unit; ULN = upper limit of normal

Note: Marked abnormality criteria are defined by Grade 3 or higher events according to the Common Terminology for Adverse Events (CTCAE), Version 5.0, November 17, 2017 unless otherwise noted.

¹eGFR is calculated by $eGFR = 141 * \min(Scr/\kappa, 1)^\alpha * \max(Scr/\kappa, 1)^{-1.209} * 0.993^{Age} * 1.018$ [if female]; where Scr is serum creatinine (mg/dL), κ is 0.7 for females and 0.9 for males, α is -0.329 for females and -0.411 for males, min indicates the minimum of Scr/ κ or 1, and max indicates the maximum of Scr/ κ or 1. For derivation from values in standard units (umol/L) the κ values are 61.88 for females and 79.56 for males.

²Includes CRP and High Sensitivity (HS) CRP. Reference for marked abnormality criteria: Nehring, S.M.; Goyal, A.; Patel, B.C. (2020). StatPearls Publishing, web link:

<https://www.ncbi.nlm.nih.gov/books/NBK441843/>.

³corrected calcium will be calculated using the formula: corrected calcium (mmol/L) = 0.02 * (40 – albumin (g/L)) + calcium(mmol/L); (40 because Normal albumin level is typically assumed to be equal to 40 g/L).

⁴Immunoglobulin G criterion based on immunodeficiency literature and noted in RLZ study protocols.

⁵Glucose high criterion defined by Grade 3 and higher events according to CTCAE, Version 4.03, June 14, 2010.

Table 6–6: Vital Signs

Parameter	Abnormality Criteria
Pulse Rate (beats/minute)	≤50 and a decrease from Baseline of ≥15 ≥120 and an increase from Baseline of ≥15
Systolic Blood Pressure (mmHg)	≤ 90 and a decrease from Baseline of ≥20 ≥ 180 and an increase from Baseline of ≥20
Diastolic Blood Pressure (mmHg)	≤50 and a decrease from Baseline of ≥15 ≥105 and an increase from Baseline of ≥15
Temperature	>101 °F (38.3 °C)
Body Weight	≥ 10% decrease from Baseline ≥ 10% increase from Baseline

Table 6–7: Electrocardiogram

Parameter	Abnormality Criteria
QT interval (ms)	≥500ms
	≥60ms increase from Baseline

Parameter	Abnormality Criteria
QTc(F) (ms)	≥500ms
	≥60ms increase from Baseline
PR interval (ms)	Treatment-emergent value >200ms
QRS interval (ms)	Treatment-emergent value >100ms
Heart rate (bpm)	<50bpm
	>120bpm

Abbreviations: bpm = beats per minute; ms = milliseconds; QTc(F) = Fridericia corrected QT interval;

Note: Treatment-emergent is defined as meeting the criteria at any post-Baseline visit after the first infusion of study medication and within 56-days of the last infusion and not meeting the same criteria during Baseline

6.6 Appendix 6: Genetics

Biomarker analyses may evaluate genetic features and epigenetic changes associated with the cause, progression, and appropriate treatment of LGI1 AIE.

Use and Analysis of DNA

- Genetic variation may impact a participant's response to study medication, susceptibility to, and severity and progression of disease. Variable response to study medication may be due to genetic determinants that impact drug absorption, distribution, metabolism, and excretion; mechanism of action of the drug; disease etiology; and/or molecular subtype of the disease being treated. Therefore, where local regulations and IRB/IEC allow, a blood sample will be collected for DNA analysis from consenting participants.
- Deoxyribonucleic acid samples and exploratory biomarker samples will be used for research related to cause, progression, and appropriate treatment of LGI1 AIE. They may also be used to develop tests/assays including diagnostic tests related to rozanolixizumab and LGI1 AIE. Genetic research may consist of the analysis of one or more candidate genes or the analysis of genetic markers throughout the genome.
- Deoxyribonucleic acid samples will be analyzed for genetic and epigenetic changes that may promote understanding of the cause, progression, and appropriate treatment of LGI1 AIE. Additional analyses may be conducted if it is hypothesized that this may help resolve issues with the clinical data.
- The samples may be analyzed as part of a multi-study assessment of genetic factors involved in the response to the study medication to understand study disease or related conditions.
- The results of genetic analyses may be reported in the clinical study report or in a separate study summary.
- The sponsor will store the DNA samples in a secure storage space with adequate measures to protect confidentiality.

The samples will be retained while research on study medication continues but no longer than 20 years or other period as per local requirements.

